### **10.2.2 Vital Signs**

Vital signs (weight, blood pressure, respiratory rate, pulse rate and temperature) will be obtained as noted in the calendar (Section 8).

### **10.2.3 Safety Laboratory Determinations**

Laboratory evaluations will be performed as noted in the calendar (Section 8).

## **10.3 Stopping Rules**

The protocol has no formal stopping rules.

# **11 STATISTICAL CONSIDERATIONS**

### **11.1 Primary Objective**

The total sample size is 15 patients. The null hypothesis is that median PSA-PFS is 3 months. With an alternative hypothesis that median PSA-PFS is 12 months, and assuming PSA-PFS is exponentially distributed, a sample size of 15 provides 90% power at one-sided alpha = 0.05. The median progression-free survival in the PROfound trial of olaparib treated patients was 7.4 months for Arm A (ie patients with BRCA1, BRCA2 or ATM alterations). This trial evaluated patients who's cancer was highly refractory and had more advanced disease. The median PFS in the TOPARP-A trial was 9.8 months in biomarker selected patients. In the ROAR trial, the patients have early disease which is hypothesized to be more responsive to treatment. We hypothesize that the median PFS will be longer than that observed in prior studies where olaparib was tested in a more advanced setting.

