## 1 OBJECTIVES

### 1.1 Primary Objective and Endpoint

1.1.1 To assess PSA progression-free survival (PSA-PFS).

Endpoint: the levels of PSA will be monitored monthly for comparison to baseline levels until the time of PSA progression, as defined by Prostate Cancer Working Group 3 (PCWG3) criteria (See Appendix B).

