#### **4.4 Study Duration**

Expected enrollment duration is 12 months, patients will remain on study treatment until PSA progression defined by PCWG3 (unless they meet the criteria for continued treatment outlined in section 6.4.1), with 2 years of follow up after study treatment. We anticipate a total of 2-3 years until completion of the clinical trial.

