# **10 CRITERIA FOR EVALUATION AND ENDPOINT**

## **10.1 Efficacy**

Patients must receive one full cycle of rucaparib and have PSA assessed after that cycle to be evaluable for efficacy. Patients who do not meet evaluable criteria will be replaced.

PSA levels will be monitored monthly while on treatment for comparison to baseline levels with the objective of assessing the proportion of patients with a 50% reduction in PSA levels (PSA50).

PSA progression-free survival (PSA-PFS) is defined as the time from study enrollment until the time of PSA progression as defined by PCWG3 criteria or death.

Patients who start another anti-cancer treatment prior to PSA progression or who complete one year of follow-up without PSA progression will have their data censored at that time point.

Overall survival is defined as the time from study enrollment until death. Survival will be monitored while on study and every 90 days for 2 years after study discontinuation.

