### **PSA Progression**

PSA should be monitored at the beginning of every cycle. Any rise in PSA during the first 12 weeks of treatment should be monitored but should not be deemed evidence of progression. Record the percent change from baseline at 12 weeks. After a decline from baseline: record time from start of therapy to first PSA increase that is  $\geq 25\%$  and  $\geq 2$  ng/mL above the nadir, and which is confirmed by a second value  $\geq 3$  weeks later (i.e., a confirmed rising trend).

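### Section 11.1 names no test and no source for its 3-month PSA-PFS null, and the PSA rules in Appendix B leave the error rate of that comparison open

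*Combined protocol and SAP*

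**What the plan says.** Section 11.1 sets the null ("The null hypothesis is that median PSA-PFS is 3 months"), an alternative median of 12 months, exponential times, 15 patients, 90% power and a one-sided 5% level. It names no test or decision rule. The two medians it cites, 7.4 and 9.8 months, come from studies of olaparib and are used to argue for a longer PFS on treatment; neither supports 3 months. Section 11.2 adds only Kaplan-Meier estimates with confidence intervals.

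Section 1.1 defines the endpoint by PCWG3 and refers to Appendix B: "the levels of PSA will be monitored monthly for comparison to baseline levels until the time of PSA progression". Appendix B says: "Any rise in PSA during the first 12 weeks of treatment should be monitored but should not be deemed evidence of progression". Its only PSA event rule (a rise of at least 25% and 2 ng/mL above the nadir, confirmed at least 3 weeks later) opens: "After a decline from baseline: record time from start of therapy to first PSA increase". For other men it asks only for the percent change at 12 weeks.

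The clocks differ. In Section 10.1, PSA-PFS "is defined as the time from study enrollment until the time of PSA progression"; Appendix B counts from the start of therapy. Section 10.1 censors two groups: "Patients who start another anti-cancer treatment prior to PSA progression", and those who "complete one year of follow-up without PSA progression will have their data censored at that time point". It does not say when that year starts, and Section 4.4 uses the term for time after treatment ("with 2 years of follow up after study treatment").

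**The concern.** Beating a 3-month median is the trial's only formal efficacy comparison. A bar of 2.76 months covers 92% of that median (2.76/3), so the null curve and the endpoint rule do not describe the same quantity. A man whose PSA rises steadily from the first dose has, on the literal words of Appendix B, no PSA event. He is then censored under Section 10.1, which favours the drug. How much this matters depends on the test, the first visit that can count and the scoring of men with no decline. The text fixes none of these.

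**Working it through.** **Inputs.** Section 11.1: null median 3 months, alternative 12, exponential, n = 15, one-sided 5%. Section 8: PSA every 28 days (plus or minus 3). Appendix B: 12-week bar. Section 10.1: censoring at one year, taken here as month 12 from enrollment (an assumption). One month = 30.44 days, so 84 days = 2.76 months and 112 days = 3.68 months.

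**Reproducing the 90%.** 3-month PSA-PFS is 0.50 under the null and 2^(-3/12) = 0.841 under the alternative. By normal approximation, n = ((1.645 × 0.5 + 1.2816 × √(0.841 × 0.159)) / 0.341)² = 14.35, so 15, with 91.3% power.

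**The same design under other tests.**
- Exact binomial, reject at 11 or more of 15: P(Bin(15, 0.5) ≥ 11) = 5.9%; power 92%.
- Exact binomial, reject at 12 or more: error 1.8%; power 79%.
- Kaplan-Meier one-sided 95% lower limit at 11/15: 0.546 on the plain scale (rejects 0.50) but 0.493 on the log-log scale (does not).
- One-sample log-rank, censored at month 12: Z = (O − E)/√E, with O the observed events and E = (ln 2 / 3) × total follow-up, rejecting below −1.645. Simulated error 3.5%, power 99.7%.

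**Effect of the 12-week bar, true median 3 months.** PSA events before 2.76 months are moved to the first time they can count.

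| First countable PSA | Log-rank error |
|---|---|
| No bar | 3.5% |
| Bar, continuous time | 7.9% |
| 28-day visits, C4D1 (day 84) counts | about 11% |
| 28-day visits, C5D1 (day 112) is first | about 18% |

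The bar does not inflate a 3-month landmark test if C4D1 counts: early events are recorded by day 84. Reading at that visit rather than at exactly 3 months gives 2^(-2.76/3) = 0.529 and P(Bin(15, 0.529) ≥ 12) = 3.0%. If C5D1 is first, no PSA event can be recorded by month 3, and the test rejects whatever the drug does, barring deaths. Appendix B does not say which applies, and the calendar lets C4D1 fall on either side of day 84.

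**Men with no decline, scored literally.** Assume 1, 2 or 3 such men of 15, with the others at a 3-month median. For the landmark test with m such men and cut-off c, error = P(Bin(15 − m, 0.5) ≥ c − m).

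| Test | No window effect, m = 1/2/3 | 12-week window added (continuous time) |
|---|---|---|
| Landmark, ≥12 | 2.9/4.6/7.3% | as left |
| Landmark, ≥11 | 9.0/13.3/19.4% | as left |
| Log-rank, censored at month 4 | 5/8/12% | 11/16/22% |
| Log-rank, censored at month 6 | 6/12/20% | 14/22/35% |
| Log-rank, censored at month 12 (worst case) | 11/30/61% | 23/52/86% |

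The right-hand log-rank figures combine two mechanisms and should not be attributed to either alone.

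**The case against.** The stated power is attainable, so a reader might infer that the sample size is wrong; it is not. The tests that come near 90% are 3-month proportion tests, and the bar leaves those alone if C4D1 counts. A reader might also infer that about 47% of the null's events (1 − 2^(-2.76/3)) are lost. They are delayed to the first countable visit, not lost, and deaths count throughout. These replies limit the window point, but they depend on a test and a visit rule that the protocol does not state.

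On men with no decline, Sections 1.1 and 10.1 define progression by the cited PCWG3 criteria, and nothing says that Appendix B overrides them. The confirmation visit (Section 9.3) is for any suspected PSA progression and does not require a prior fall. That stands: the documents show an incomplete appendix, not that such men would in fact go unscored. The baseline-referenced PSA limit in Section 6.4.1 does not fill the gap, because it governs staying on treatment.

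The differences in clock are small. Section 12 allows five working days from registration to treatment, about 7 calendar days if enrollment means registration. The one-year rule follows shortly after the enrollment-based definition, so enrollment is its natural origin. Both need only a clarifying phrase.

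**Conclusion.** The concern holds and should be fixed. It needs no assumption to see that the test is unnamed, the 3-month null unsourced, the appendix rule limited to men with a decline, and the time origins different. Depending on the test, the same design has 79% to 99.7% power. When the true median is 3 months, the bar takes a conventional log-rank test from 3.5% error to between 7.9% and about 18%. A landmark test at 3 months is either unaffected by the bar or uninformative, according to whether C4D1 counts.

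The figures for men with no decline are conditional on a literal reading of Appendix B, an assumed 1 to 3 men, and an assumed censoring time. A reader might take 86% as the trial's false-positive rate. The documents do not support that: it requires three such men, all followed event-free to month 12 without another treatment, a log-rank test the protocol does not name, and the 12-week window on top. The textual gaps are certain; the size of their effect is not.

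**What to change.** 1. For the PSA-PFS analysis only, add to Appendix B an event rule for men with no decline, measured from baseline after week 12 and consistent with the cited criteria. State whether the C4D1 PSA can count. Use one time origin in Section 10.1 and Appendix B, and say when the one year of follow-up begins.
2. In Section 11.1, name a test that respects the window and the visits, and restate its error and power. Two examples:
   - A one-sample log-rank whose expected events use the null hazard at each countable visit, h = 1 − S0(visit)/S0(previous countable visit), where S0 is the null curve (S0 = 1 at time zero), with variance Σh(1 − h): error about 4% whether C4D1 or C5D1 is first, power 99.7%.
   - An exact test of 6-month PSA-PFS, null 2^(-6/3) = 25%, reject at 8 or more of 15: error 1.7% and power 96%, or 3.3% and 97% if read at day 168. It keeps the same exponential null curve, and the handling of men censored earlier must be stated.
3. Give the source of the 3-month null, or justify it under the Appendix B rule.
4. Make the change before PSA-PFS data are examined. Otherwise report it as a sensitivity analysis beside the analysis as now written; the trial is open label and at protocol Version 6.

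The cost is wording in Sections 10.1 and 11.1 and Appendix B, and a recalculation of the stated 90% power. No extra patients or visits are needed.

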8. If treatment is discontinued prior to PSA progression, PSA testing will continue throughout follow-up until PSA progression or start of another treatment. Patients who have PSA progression prior to discontinuing treatment do not need to have PSA testing performed during follow-up.
9. Rucaparib will be administered as described in Section 6.
10. Blood collection for biomarkers will be collected at screening, C3D1, C7D1, and confirmed PSA disease progression ( $\pm 7$  days), if applicable, or at EOT visit (whichever occurs first).

11. For patients enrolled with an intact prostate, urine collection for biomarkers will be collected at screening, C3D1, C7D1, and confirmed PSA disease progression ( $\pm$  7 days), if applicable, or at EOT visit (whichever occurs first).
12. Archival tissue will be collected at screening (if available). Archival tissue should not be cut until instructed by the central lab.
13. Genomic or genetic testing for 'BRCAness' will be confirmed with either blood or tissue based testing.
14. An optional fresh tissue biopsy may be obtained at PSA Progression Confirmation Visit ( $\pm$  28 days) for subjects with radiographic disease progression.
15. CT scans of the chest/abdomen and pelvis and NM bone scans will be done at the time of PSA Progression Confirmation Visit ( $\pm$  28 days) as defined in section 10.1.
16. Follow-up should occur every 90 days ( $\pm$  14 days) for 2 years following End of Treatment as per standard of care (section 9).
17. Coagulation Panel includes PT/INR, PTT.
18. The end of treatment visit should occur within +/-3 days of the decision to discontinue treatment. If this visit overlaps with a regularly scheduled visit, only the procedures listed in the calendar for the EOT visit will be performed.
19. To be performed only if the subject has completed hormone therapy. Screening testosterone may be performed within 84 days of study enrollment.
20. Only patients who have suspected PSA progression during a regular study visit will have testing to confirm PSA progression at their next regularly scheduled visit. **Before continuation of treatment after confirmed PSA progression, the patient must agree to sign the Treatment After Progression Informed Consent Form.** Patients may complete the assessments required for PSA progression in conjunction with the next regularly scheduled cycle visit or at EOT.

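### Section 11.1's 90% power and alpha 0.05 rest on an exponential PSA-PFS that puts 47% of null events in the 12 weeks where Appendix B allows no PSA progression, and no test is named to which the figures belong

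*Combined protocol and SAP*

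**What the plan says.** Section 11.1 sets a null median PSA-PFS of 3 months and an alternative of 12 months and states, "assuming PSA-PFS is exponentially distributed, a sample size of 15 provides 90% power at one-sided alpha = 0.05". The Study Summary gives the same sample size, power and alpha. Neither place names a test, a rejection boundary or an analysis time. Section 11.2 adds Kaplan-Meier estimates with confidence intervals for PSA-PFS, and no other method is named for it.

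Section 1.1 refers the endpoint to Appendix B, whose PSA Progression text says: "Any rise in PSA during the first 12 weeks of treatment should be monitored but should not be deemed evidence of progression". It also says "PSA should be monitored at the beginning of every cycle" and "Record the percent change from baseline at 12 weeks". After a decline from baseline, the instruction is to "record time from start of therapy to first PSA increase that is" at least 25% and at least 2 ng/mL above the nadir, with confirmation three or more weeks later.

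Section 10.1 uses a different starting point: PSA-PFS "is defined as the time from study enrollment until the time of PSA progression as defined by" PCWG3, or death. Patients who "complete one year of follow-up without PSA progression will have their data censored at that time point". In Section 8 a cycle is 28 days, give or take 3, and footnote 20 ties confirmation to scheduled visits: "Only patients who have suspected PSA progression during a regular study visit will have testing to confirm PSA progression". Section 12 asks that treatment start within five working days of registration.

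**The concern.** An exponential distribution has events from time zero. With a 3-month median, nearly half of them fall before week 12, yet in that period the endpoint can record only deaths. Nothing in the documents adjusts the null, the distribution, alpha or power for this.

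The 3-month null median lies about one week after the 12-week period closes. For the recorded median to be 3 months, deaths aside, half the men would need progression dated within that week. A reader of Section 11.1 would take a positive result as evidence at the 5% level with 90% power. What those figures mean depends on a test that is not named and on how a single PSA value is treated.

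**Working it through.** **Inputs.** From Section 11.1: n = 15, medians 3 and 12 months, exponential, one-sided 0.05. From Appendix B: the 12-week rule and a PSA at the start of each cycle. From Section 8: 28-day cycles, ±3 days. From Section 10.1: time from enrollment, and censoring at one year. From Section 12: start within five working days of registration.

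**Conventions and assumptions.** One month is 30.44 days, so 84 days = 2.76 months and 3 months = 91.3 days. First dose is Day 1. The ±3 days do not accumulate over cycles. Registration is taken as enrollment. Five working days are at most 7 calendar days. Deaths are ignored.

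**1. Reproducing the plan's figure.** Under the exponential, S(3) = 2^(−3/3) = 0.500 (null) and 2^(−3/12) = 0.841 (alternative).
- z test of S(3) against 0.5: Φ[(0.341 − 1.645·√(0.25/15)) / √(0.841·0.159/15)] = Φ[(0.341 − 0.212)/0.0944] = 0.913. With 14 men it is 0.892.
- Arcsine version: Φ[2√15·(asin√0.841 − asin√0.5) − 1.645] = Φ(2.906 − 1.645) = 0.896.
- One-sample log-rank against the exponential null: simulated power 0.913 with 7 men and 0.997 with 15. This does not explain n = 15.

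Of the calculations tried, only an approximate test at 3 months matches the stated figures.

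**2. Share of events before week 12.**
- Null: 1 − 2^(−2.76/3) = 0.471; × 15 = 7.1 men.
- Alternative: 1 − 2^(−2.76/12) = 0.147; × 15 = 2.2 men.
- PSA progressions that Appendix B permits there: 0.

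**3. Exact rules on 15 men under the plan's own exponential.**

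| Progression-free at 3 months | Size at S(3) = 0.500 | Power at S(3) = 0.841 |
|---|---|---|
| 11 or more | 0.059 | 0.924 |
| 12 or more | 0.018 | 0.794 |

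Neither row gives both 0.05 and 90%. With a Kaplan-Meier interval, the interval type selects the row. At 11/15 the one-sided 95% lower limit is 0.546 (plain Greenwood), 0.493 (log-log) or 0.489 (Clopper-Pearson). At 12/15 all three exceed 0.5 (0.630, 0.561, 0.560).

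**4. Other shapes that respect the 12-week rule.** If early events are simply moved to week 12, S(3) is still 0.841 and the 12-of-15 power is still 0.794. If there is no hazard before week 12 and an exponential after it with a 12-month median, S(3) = 2^(−(3 − 2.76)/(12 − 2.76)) = 0.982, and the 12-of-15 rule has power above 0.999. Its size stays 0.018 in both cases if the recorded median is 3 months under the null.

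**5. A test that does rely on the exponential null.** One-sample log-rank, (O − E)/√E, n = 15, censored at 12 months, nominal 0.05, recorded median 3 months:
- continuous exponential: 0.035;
- early events moved to week 12: 0.079;
- no hazard before week 12, then exponential: near 0.

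**6. Visits around month 3.** C4D1 is 3 × 28 = 84 days after first dose, which is Day 85, with a window of Day 82 to 88. C5D1 is at 112 days, or 3.68 months. C4D1 is therefore the only scheduled PSA that can inform 3-month PSA-PFS.
- A draw 1 to 3 days early (Day 82 to 84) lies inside the first 12 weeks.
- From start of therapy, C4D1 comes at 87 days at the latest, before month 3. From enrollment it can come at 84 + 3 + 7 = 94 days, after month 3 (91.3 days).
- If the C4D1 value does not count, recorded 3-month PSA-PFS is 1 apart from deaths, and comparing it with 0.5 tells the reader nothing about the drug.

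**The case against.** The strongest reply is that the one calculation that fits n = 15 is a 3-month landmark test, and the 12-week rule leaves its size unchanged when the recorded median is truly 3 months. Kaplan-Meier, the only method named, leads to much the same test. The gap between 0.059 and 0.018 is ordinary discreteness in 15 men. The log-rank values concern a test that the plan never mentions and that does not fit its sample size. All of this stands. It rules out saying that the 12-week rule inflates alpha in this trial. Those values show only that a test leaning on the exponential null would not hold 0.05, with the direction set by the shape.

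Four stronger readings are tempting, and the documents do not support them:
- *Power is below 90%, or 15 men are too few.* Step 4 shows that power can be far higher under a shape that respects the rule.
- *No exact rule can meet both stated figures.* That holds under the plan's exponential. It fails under the delayed shape, where 12 of 15 has size 0.018 and power above 0.999.
- *The trial would falsely reject if C4D1 does not count.* The null in Section 11.1 concerns the recorded endpoint. If C4D1 cannot count, the recorded median cannot be 3 months, deaths aside, so rejecting that null is not a type I error. Calling it one requires a latent progression time that the protocol does not define. The comparison is uninformative, which is a different fault.
- *C4D1 generally falls in the excluded period.* On schedule it is Day 85, just outside. The doubt is confined to early draws and the time origin, and the 94-day case combines the longest start delay with the latest visit.

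**Conclusion.** Wrong as written; should-fix. The distribution from which Section 11.1 derives its figures cannot be that of the endpoint in Appendix B: it places 47% of null events (7.1 of 15) and 15% of alternative events (2.2 of 15) where no PSA event is allowed. The stated 90% and 0.05 are recovered only approximately, by a 3-month test that the plan does not name. Under the plan's own model, exact versions of that test give 0.059 with 0.924 or 0.018 with 0.794. That test also depends on one PSA value whose admissibility when drawn early, and whose position before or after month 3, the documents leave open.

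This rests on the conventions listed in the working and on early deaths being rare in this population. The shares before week 12 need only the stated medians and the exponential. The calendar results also need registration to be enrollment.

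**What to change.** 1. Use one time origin for PSA-PFS in Section 10.1 (now enrollment) and Appendix B (now start of therapy).
2. State whether the C4D1 PSA can count toward the endpoint, including when it is drawn 1 to 3 days early.
3. In Section 11.1 and the Study Summary, name the primary test, its rejection boundary (or the confidence-interval type that fixes it) and its analysis time.
4. Replace the quoted alpha and power with values computed for that test under a distribution with no PSA events before week 12 and PSA every 28 days. State the assumed shape, since step 4 shows how much power depends on it.

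The cost is wording in four places and one short calculation. Sample size and visits need not change. The quoted figures may become less favourable.

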### **11.2 Secondary Objectives**

Descriptive analysis methods will be used to analyze tabulated safety characteristics. Kaplan-Meier methods and associated confidence intervals will also be used to analyze PSA progression-free survival and OS. The proportion of subjects who achieve PSA50 will be reported along with a 95% confidence interval. The proportion of subjects with an undetectable PSA after initiation of PARP therapy at 6 and 12 months will be assessed using Kaplan-Meier methods and associated confidence intervals. The proportion of subjects who exhibit an objective response will be reported along with an exact binomial confidence interval.

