Reference therapy	None
Statistical Methodology	
Primary Objective: The total sample size is 15 patients. The null hypothesis is that median PSA-PFS is 3 months. With an alternative hypothesis that median PSA-PFS is 12 months, a sample size of 15 provides 90% power at one-sided alpha = 0.05. The proportion of subjects who achieve PSA50 will be reported along with a 95% exact binomial confidence interval.
 
Descriptive analysis methods will be used to analyze tabulated safety characteristics. Kaplan-Meier methods will be used to assess the proportion of patients with an undetectable PSA after initiation of PARP therapy.

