### 1.2 Secondary Objectives and Endpoint

1.2.1 To assess the safety of rucaparib in patients with biochemically recurrent hormone-sensitive prostate cancer.

Endpoint: adverse events will be monitored regularly during patient enrollment and follow up to assess the toxicity of rucaparib using validated CTCAE v5.0 criteria.

1.2.2 To assess the proportion of patients with a 50% reduction in PSA levels (PSA50) compared to the baseline value at the time of study enrollment.

Endpoint: the levels of PSA will be monitored monthly for comparison to baseline levels.

1.2.3 To assess the proportion of patients with an undetectable PSA after initiation of PARP therapy at 6 and 12 months.

Endpoint: the levels of PSA will be monitored monthly for comparison to baseline levels to determine when PSA becomes undetectable.

1.2.4 To evaluate overall survival (OS) in nonmetastatic hormone-sensitive prostate cancer patients treated with rucaparib.

Endpoint: Subjects will be evaluated for survival using Kaplan-Meier estimation.

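### Undetectable PSA at 6 and 12 months is assigned to Kaplan-Meier, which estimates ever undetectable by those times, and no rule covers men whose PSA testing ends

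*Combined protocol and SAP*

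**What the plan says.** Objective 1.2.3 reads: "To assess the proportion of patients with an undetectable PSA after initiation of PARP therapy at 6 and 12 months". Its endpoint line adds that monthly PSA is compared with baseline "to determine when PSA becomes undetectable". Section 11.2 assigns the method: "The proportion of subjects with an undetectable PSA after initiation of PARP therapy at 6 and 12 months will be assessed using Kaplan-Meier methods". The Study Summary gives the same method without time points: "Kaplan-Meier methods will be used to assess the proportion of patients with an undetectable PSA after initiation of PARP therapy".

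The two neighbouring response endpoints are handled differently. For PSA50 the summary says "The proportion of subjects who achieve PSA50 will be reported along with a 95% exact binomial confidence interval", and for objective response Section 11.2 says "The proportion of subjects who exhibit an objective response will be reported along with an exact binomial confidence interval".

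On PSA testing, note 8 of the Study Calendar says: "Patients who have PSA progression prior to discontinuing treatment do not need to have PSA testing performed during follow-up". The same note and Section 9.5 continue testing for men who stop treatment before progression, but only until progression or another treatment. Men with suspected progression "will have testing to confirm PSA progression at their next regularly scheduled visit" (note 20). Men who stay on rucaparib after progression under Section 6.4.1 keep the full assessment schedule, PSA included.

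The only censoring sentence is in Section 10.1. It follows the PSA-PFS definition and covers men who start another anti-cancer treatment or complete a year without PSA progression. It does not say how a man who has progressed is handled for the undetectable-PSA endpoint.

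**The concern.** There are two problems. First, the stated objective and the named method point to different quantities. A first-attainment curve never comes back down: a man undetectable at month 3 and detectable again by month 12 still counts at month 12. A reader shown a 12-month figure may well take it as the share of men undetectable at one year.

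Second, for the *by* reading, one minus Kaplan-Meier differs from a plain proportion only through censoring, so the censoring rule decides what the method adds. The plan gives none for men whose testing ends at progression. Censoring them treats them as still able to become undetectable at the rate of the men who remain. Yet under Appendix B, progression after a decline is a confirmed PSA at least 25% and at least 2 ng/mL above the nadir.

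In a single-arm trial of 15 men, both effects can only raise the reported figure. What is at stake is the reading of one descriptive secondary endpoint.

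**Working it through.** **Plan's own figure.** The documents give no assumed rate or precision for this endpoint, so there is nothing to reproduce. The 90% power in Section 11.1 concerns PSA-PFS and is not in question here.

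**How many men the missing rule could touch.** Section 11.1 assumes exponential PSA-PFS with a median of 12 months under the alternative. Expected progressors among 15 are 15 × (1 − 0.5^(6/12)) = 4.4 by month 6 and 15 × (1 − 0.5^(12/12)) = 7.5 by month 12.

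***At* against *by*, with no censoring.** Suppose 3 of 15 men are ever undetectable by month 12 (assumed). One minus Kaplan-Meier is 3/15 = 20%. If 0, 1 or 2 of the three are detectable again by then, the proportion *at* month 12 is as follows.

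| Detectable again | Proportion at month 12 | Exact 95% interval |
|---|---|---|
| 0 | 3/15 = 20% | 4% to 48% |
| 1 | 2/15 = 13% | 2% to 40% |
| 2 | 1/15 = 7% | 0% to 32% |

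**Direction of the censoring effect.** Take 15 invented men. Three are first undetectable at months 2, 4 and 8. Eight progress and stop testing at months 3, 3, 3, 5, 5, 7, 7 and 9. Four are followed to month 12. If progressors are censored, the risk sets at the three events are 15, 11 and 6:

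- Month 6: 1 − (14/15)(10/11) = 15.2%, against 2/15 = 13.3%.
- Month 12: 1 − (14/15)(10/11)(5/6) = 29.3%, against 3/15 = 20.0%.

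With the progressors kept in the risk set, Kaplan-Meier returns 13.3% and 20.0% exactly. The example shows direction only; its counts were chosen.

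**Size under the design assumptions.** Assumed, not in the documents:

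- a true 20% attain an undetectable PSA by month t, before testing ends;
- attainment is independent of progression;
- every progressor stops treatment and is censored.

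Taken or adapted from the documents: no progression before week 12 (84 days = 2.76 months, Appendix B); a last PSA about one month after progression (note 20); medians m of 12, 9.8 and 7.4 months (Section 11.1).

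The progression hazard is b = ln 2/(m − 2.76) from month 2.76, so censoring starts at month 3.76. With attainment hazard h(s) and cumulative hazard H(s), solve

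∫₀ᵗ h(s) exp(−H(s) − b·max(0, s − 3.76)) ds = 0.20,

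then read one minus Kaplan-Meier as 1 − exp(−H(t)).

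Worked case: m = 12, constant rate a, t = 12. Here b = 0.693/9.24 = 0.0750, and the solution is a = 0.0227. Check:

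- attained by month 3.76: 1 − exp(−0.0855) = 0.082;
- attained later: 0.918 × (0.0227/0.0977) × (1 − exp(−0.0977 × 8.24)) = 0.118;
- total: 0.200.

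Then H(12) = 0.273 and 1 − exp(−0.273) = 23.9%.

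| Attainment pattern, read at month 12 (true 20%) | m = 12 | m = 9.8 | m = 7.4 |
|---|---|---|---|
| Constant rate | 23.9% | 25.0% | 27.3% |
| Rate halves every 4 months | 21.8% | 22.3% | 23.3% |
| Rate halves every 2 months | 20.8% | 21.0% | 21.4% |
| First 12 weeks only | 20.0% | 20.0% | 20.0% |

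At month 6 the constant-rate row reads 20.6%, 20.7% and 21.1%. If half of the progressors stay on treatment and tested (assumed), the month-12 reading at m = 12 falls to 22% for a constant rate and 21% for a rate halving every 4 months.

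**The case against.** The strongest reply is that the plan is coherent on the *by* reading. The endpoint line speaks of when PSA becomes undetectable, Kaplan-Meier is a time-to-first-event method, and *at* 6 and 12 months is ordinary wording for reading a curve at two landmarks. This has force: the documents do not show that status at the visit was intended. It does not settle the matter, because the objective and its endpoint line can still be read as two quantities.

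The second reply is that a bias has not been demonstrated. That also stands. The plan nowhere says progressors are censored, and treatment with full PSA testing may continue after progression for men who meet the Section 6.4.1 criteria. The upper end of the illustration needs steady attainment for a year and every progressor stopping treatment.

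Third, the Section 10.1 censoring sentence is not expressly limited to PSA-PFS and could be read to cover men who start another therapy. It still does not reach men who have progressed.

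Fourth, Kaplan-Meier has a proper use for men lost to follow-up, and counting them as not undetectable pulls the estimate down. That is a real cost. Finally, the plan gives no PSA limit that defines undetectable, so any version of the analysis needs one.

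**Conclusion.** The point holds as a minor correction. The target is ambiguous between *by* and *at*, with the endpoint line leaning toward *by*. Kaplan-Meier is a poor choice for either: it does not estimate status at a visit, and for first attainment it adds to a simple count only through a censoring rule that is missing where it matters.

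If progressors are censored in the usual way, one minus Kaplan-Meier equals or exceeds the true proportion. For a true 20% at month 12 and the design median of 12 months, the shift is 0 to 4 points under the assumptions listed, against an exact interval of 4% to 48% for 3 of 15. It is zero if progressors stay in the risk set or if all attainment precedes progression.

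A reader might infer that the planned figure is known to be inflated, or inflated by a large amount. The documents support neither. The first depends on a censoring choice the plan does not state. The second needs short progression times: a separate simulation with a true 20%, and every non-responder's testing ending at progression, averages 42% at month 12 if their median is the null value of 3 months, but 24% at 12 months. The 9.8- and 7.4-month medians come from more advanced disease, which Section 11.1 expects this trial to exceed. The primary PSA-PFS test is unaffected.

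**What to change.** In 1.2.3, Section 11.2 and the Study Summary, state *by* or *at* and replace Kaplan-Meier.

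- **If *by*** (the reading the endpoint line favours): report the number of evaluable men with a first undetectable PSA by 6 and by 12 months, with an exact binomial 95% interval. Count men who progressed and are no longer tested, started other anti-cancer therapy, or died, without an earlier undetectable value, as not undetectable. Alternatively, use a cumulative incidence function with those as competing events and only loss to follow-up or withdrawal censored.
- **If *at***: report the number undetectable at the PSA closest to month 6 and to month 12 within a stated window, over all evaluable men, with an exact binomial interval and the same counting rule. Report how many men have no PSA in the window. Off-treatment visits every 90 days need a half-width of at least 45 days, or 59 days to allow for the ±14-day leeway (90 + 14 + 14 = 118; 118/2 = 59). The two wider windows do not overlap (183 + 59 = 242, before 365 − 59 = 306). Visits can be as close as 90 − 28 = 62 days, so two values may fall in one window; the closest-value rule then chooses.

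State the PSA limit that counts as undetectable. The cost is a few sentences and no new data. The reported proportion may be lower, and counting lost men as not undetectable is conservative.
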